#### **AMENDMENTS**

MATIS version 4.0 dated 2nd November 2022

IRAS: 282552 Page **5** of **57** 

The following amendments and/or administrative changes have been made to this protocol since the implementation of the first approved version:

Amendment Number	Date of Amendment	Protocol Version Number	Type of Amendment	Summary of Amendment
1	14.08.2020	1.8	Substantial Amendment	The opening site will be Imperial College Healthcare NHS Trust in the United Kingdom. Additional UK based sites for the trial will include Hillingdon, Royal Free Hospital, Northwick Park and Chelsea and Westminster added according to trial progress. 171 (57 per arm) patients with COVID-19 pneumonia will be recruited to Stage 1, if the trial progresses to Stage 2 an additional maximum of 285 (95 per arm) will be recruited, resulting in a potential sample size of 456 if three trial arms continue for the whole trial (152 per arm). These numbers have been chosen to provide a power of 90% with a maximum 5% chance of an intervention arm being recommended when it provides no improvement over control (5% one-sided family-wise error rate).
2	29.10.2020	1.9	Substantial Amendment	Additional UK sites Leeds and Leicester. Inclusion criteria: CRP now less than or equal to 30 mg/L. Exclusion criteria: removed end stage renal failure, clarified patients on home NIV/CPAP now eligible. Dialysis patients randomised to Ruxolitinib (RUX), will receive only 20mg on dialysis days Week 1, then 10mg on dialysis days Week 2. Pharmacokinetics will be assessed at Baseline, before each dialysis and Day 28. RUX dose for these patients will be assessed after 10 dialysis patients complete Day 14. Research samples will be processed and analysed at Immunology of Infection lab at Imperial College London, St Mary's Campus. Added location of research lab. Updated PIS. Updated early discharge. Trial Team and oversight committees updated. Updated unblinding.
3	24/02/2021	2.0	Non- Substantial	Correcting the name of sites from Northwick Park Hospital to London North West University
			Amendment	Healthcare NHS Trust (Northwick Park Hospital and Ealing Hospital)

IRAS: 282552 Page **6** of **57** 

2	31/03/2021	2.1	Non- Substantial Amendment	Addition of UK site: Sheffield Teaching Hospitals NHS Foundation Trust

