#### 2.2 SECONDARY OBJECTIVES

- Determine the efficacy of RUX or FOS to reduce mortality
- Determine the efficacy of RUX or FOS to reduce the need for invasive ventilation and/or ECMO
- Determine the efficacy of RUX or FOS to reduce the need for non-invasive ventilation including CPAP or high flow nasal oxygen
- Determine the efficacy of RUX or FOS to reduce the proportion of patients suffering clinically significant oxygen desaturation
- Determine the efficacy of RUX or FOS to reduce the need for renal replacement therapy
- Determine the efficacy of RUX and FOS to reduce the incidence of venous thromboembolism COVID-19 pneumonia
- Determine the efficacy of RUX and FOS to improve the severity of COVID19 pneumonia on a modified
   WHO COVID19 Ordinal Scale
- Determine the efficacy of RUX or FOS to reduce the level of inflammatory biomarkers
- Determine the efficacy of RUX or FOS to reduce blood ferritin, CRP, LDH and D-dimer
- Determine the efficacy of RUX or FOS to reduce the level of serum creatinine.
- Determine the efficacy of RUX or FOS to reduce duration of hospital admission
- Evaluate the safety of RUX and FOS for COVID19 pneumonia

IRAS: 282552 Page **21** of **57** 

[figure not shown]

- Determine the impact of RUX or FOS to reduce the development of the post-acute COVID-19 syndrome
  in patients who presented with mild-moderate COVID-19 pneumonia
- Determine the impact of RUX or FOS on long term (12-18 months) survival
- Determine the ability of RUX or FOS to reduce the development of the post-acute COVID-19 syndrome
  in patients who presented with mild-moderate COVID-19 pneumonia
- Assess impact of signal inhibitors (RUX or FOS) on health related quality of life at 6 and 12, 18 months post COVID-19

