#### 7.7 DOSE MODIFICATIONS FOR RUXOLITINIB

#### End stage renal failure patients

Patients with glomerular filtration rate (GFR) <15 ml/min (dialysis and non-dialysis patients) will receive 20mg three times a week the first week and for the second week 10 mg three times a week (taken at the end of dialysis if on dialysis).

Patients with GFR ≥15 ml/min to < 30 ml/min, 5 mg twice a day for 1 week, then 5 mg once a day for 1 week.

For dialysis patients, pharmacokinetic (PK) levels will be assessed before each dialysis and at Day 14 and Day 28.

Ruxolitinib dose for these patients will be assessed after 10 dialysis patients complete these doses to Day 14.

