1.9 Informal interim analysis outcomes - Completed 29th Jan 2021

At the end of the initial stage, the mean CRP values over days 1, 7, 14 and 28 (adjusted for baseline) will be calculated by treatment arm. The mean CRP will also be calculated by treatment arm and visit (adjusted for baseline). These results will form part of the evidence to verify the dose and duration of treatment for the next stage. The pre-specified criteria guiding this inference are listed in full below.

- Dose continues unchanged: For each treatment arm (RUX or FOX) the dose and duration will remain unchanged if there is an absolute mean CRP decrease of approximately 25% or more compared to SOC by day 14 and judged to be maintained by day 28.
- Dose escalation or duration increase: For each treatment arm (RUX or FOX) an adjustment to the dose and duration will be discussed if the mean CRP decrease is less than approximately 25% compared to SOC by day 14.

The results were taken into consideration along with the number of SAEs and SARs and consistency of treatment effect across subgroups including renal failure, use of immunomodulators and age group. Platelet counts and neutrophil counts were also examined over time to monitor the treatment effect in renal failure patients with a dose reduction.

The Data Monitoring Committee and chief investigator, with contribution from the unblinded senior statistician and independent statistician reviewed the unblinded efficacy data and made a recommendation on the 29th January 2021 to the Trial Steering Committee to continue to the next stage maintaining existing dosing schedule.

2. Data analysis plan – data description

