3.1 Primary outcome of the main study - Modified WHO grading

3.1.1 Definition of the primary outcome

The proportion of participants progressing from mild to severe COVID-19 pneumonia within 14 days. Where severe COVID-19 pneumonia is defined by a modified WHO COVID-19 Ordinal Score ≥ 5 (on the 9 point scale), comprising the following indicators of disease severity: Death (9) OR Requirement for invasive ventilation plus organ support (8) Requirement for invasive ventilation (7) OR Requirement for non-invasive ventilation including CPAP or high flow oxygen (6) OR O₂ saturation < 90% on \geq 60% inspired oxygen (5). These are captured in the database as follows:

Modified WHO COVID-19 Ordinal Score	Database
(9) Death	
(8) Requirement for invasive ventilation plus organ support	Has the patient required renal replacement therapy? OR Has the patient required ECMO? OR Has the patient required inotropic support? AND Has the patient required intubation and mechanical ventilation?
(7) Requirement for invasive ventilation	Has the patient required intubation and mechanical ventilation?
(6) Requirement for non-invasive ventilation including CPAP or high flow oxygen	Has the patient required NIV, CPAP or high flow nasal oxygen?
(5) O ₂ saturation < 90% on ≥60% inspired oxygen	Has the patient's oxygen saturation been < 90% on 60% inspired oxygen?

3.1.2 Statistical model at stage 1

The stage one primary analysis will consist of fitting two separate binomial regression models for the RUX vs SOC and FOS vs SOC comparisons in order that we can undertake an adjusted analysis using a propensity score approach. Specifically a generalized linear model with WHO COVID-19 status (<5 or ≥ 5) as the outcome and treatment group as a covariate. We will adjust the treatment effect for the

following prespecified covariates using a propensity score approach. The propensity score model will include:

- baseline WHO COVID-19 score (3 or 4)
- age ($<65 \text{ or } \ge 65$)
- receipt of dexamethasone (prior randomisation or up to 1 day post randomisation)
- receipt of tociluzimab (prior randomisation or up to 1 day post randomisation)

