3.2.3 Components of the modified WHO COVID-19 score

The following outcomes will be examined at day 14 and day 28 by replacing the primary outcome in the main analysis model as described in section 3.1.3:

- Death (yes/no)
- Requirement for invasive ventilation plus organ support (yes/no)
- Invasive ventilation (yes/no)

- Non-invasive ventilation including CPAP and high flow nasal oxygen (yes/no)
- Renal replacement therapy (yes/no)
- Venous thromboembolism (yes/no)

Each model will be fitted on complete cases and no imputation of missing values or sensitivity analysis will be undertaken.

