3.2.5 Continuous laboratory values

For inflammatory markers of CRP, LDH, ferritin, D-dimer and serum creatinine levels a linear mixed effect model will be used to estimate the mean difference in values between intervention arms (RUX and FOS) and SOC at each follow-up visit (day 1, day 7 and day 14). Participants will be included as a random intercept with fixed effects for time, time-by-treatment arm interaction and baseline values. Stratification variables age and site, plus receipt of known effective treatments dexamethasone and/or tociluzimab, prior vaccination against COVID-19, and receipt of paxlovid and/or molnupiravir at the time of or prior to randomisation into MATIS will also be included as fixed effects. Baseline adjusted treatment group differences with 95% confidence intervals will be presented for each time-point.

For example for CRP the model to be fitted to estimate the treatment effect at each visit up to day 14 will be:

$$\begin{split} Y_{ijt} = \ \beta_0 + \ \beta_1 R U X_{ij} + \ \beta_2 F O S_{ij} + \ \beta_3 C R P_{ij}^0 + \ \beta_4 A G E_{ij}^0 + \ \beta_5 D E X_{ij}^0 \\ + \ \beta_6 T O C_{ij}^0 + \ \beta_7 V A C_{ij}^0 + \ \beta_8 P A X_{ij}^0 + \ \beta_9 M O L_{ij}^0 \ \beta_{10} time_7 \\ + \ \beta_{11} time_{14} + \ \beta_{12} R U X_{ij} * time_7 + \ \beta_{13} R U X_{ij} * time_{14} \\ + \ \beta_{14} F O S_{ij} * time_7 + \ \beta_{15} F O S_{ij} * time_{14} + \ \beta_{16} S I T E_1 \\ + \ \beta_{17} S I T E_2 + \dots + \ \beta_{18} S I T E_{j-1} + b_{1,i} + e_{it} \end{split}$$

for

t = 1 to 3 time points (day 1, 7 and 14), i = 1 to 30 participants

 RUX_{ij} : dummy variable for treatment ($RUX_{ij} = 0 \text{ or } 1$) for participant i

 FOX_{ij} : dummy variable for treatment ($FOS_{ij} = 0 \text{ or } 1$) for participant i

 CRP_{ij}^{0} : baseline CRP value for participant i

 DEX_{ij}^0 : dummy variable for receipt of dexamethasone at the time of or prior to randomisation (includes day of randomisation or one day post randomisation) ($DEX_{ij} = 0 \text{ or } 1$) for participant i TOC_{ij}^0 : dummy variable for receipt of tociluzimab at the time of or prior to randomisation (includes day of randomisation or one day post randomisation) ($TOC_{ij} = 0 \text{ or } 1$) for participant i VAC_{ij}^0 : dummy variable for prior vaccination against COVID-19 at the time of or prior to randomisation (includes day of randomisation or one day post randomisation) ($VAC_{ij} = 0 \text{ or } 1$) for participant i

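### The renal replacement therapy endpoint counts maintenance dialysis that began before randomisation, which dilutes the treatment comparison

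*SAP*

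**What the plan says.** **Eligibility.** The amendment table records the change: "Exclusion criteria: removed end stage renal failure, clarified patients on home NIV/CPAP now eligible". The current exclusion lists (Protocol 5.3, SAP 1.3.1) name neither dialysis nor renal failure. Protocol 7.7 has its own ruxolitinib provision for "Patients with glomerular filtration rate (GFR) <15 ml/min (dialysis and non-dialysis patients" and adds: "Ruxolitinib dose for these patients will be assessed after 10 dialysis patients complete these doses to Day 14". SAP 1.9 shows that such patients were already enrolled at the informal interim analysis, where counts were examined to "monitor the treatment effect in renal failure patients with a dose reduction".

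**Objective and endpoint.** The objective in Protocol 2.2 is: "Determine the efficacy of RUX or FOS to reduce the need for renal replacement therapy". SAP 3.2.3 lists the endpoint as "Renal replacement therapy (yes/no". The database item shown in SAP 3.1.1 is "Has the patient required renal replacement therapy". None of these is restricted to therapy that starts after randomisation. In Protocol 3.3, by contrast, the hypertension and diabetes outcomes are limited to new diagnoses.

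**Analysis.** SAP 3.2.3 reuses the primary model with the outcome exchanged. The covariates in SAP 3.1.3 are arm, baseline WHO score, age group, dexamethasone, tocilizumab, vaccination, two antivirals and site. SAP 3.2.3 uses complete cases and excludes any sensitivity analysis. The kidney disease subgroup in SAP 3.1.6 applies to the primary outcome only. Randomisation is stratified by age and site (Protocol 6.2).

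**Creatinine.** SAP 3.2.5 states: "For inflammatory markers of CRP, LDH, ferritin, D-dimer and serum creatinine levels a linear mixed effect model will be used". The model adjusts for the baseline value and does not set dialysis patients apart.

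**The concern.** Maintenance dialysis is settled before randomisation, and two weeks of study drug cannot undo it. A patient who enters on dialysis and stays on it truthfully answers yes to the database item in every arm. That patient adds an event to each side of the comparison and carries no information about whether the drug prevents kidney failure.

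Two things follow. The odds ratio moves towards 1, so a real effect on new renal replacement looks smaller than it is. And because the strata do not include renal status, the number of dialysis patients will differ between arms by chance, on an endpoint where the effect itself may be only a few patients. No later step in the plan would show a reader of the results how much of either had occurred.

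**Working it through.** **The plan's own figures.** The documents give no event rate, effect size or power for renal replacement therapy, so there is nothing to reproduce for this endpoint. The primary design does reproduce. With 50% against 30%, one-sided 0.25 at stage 1, one-sided 0.027 at stage 2, and a correlation of sqrt(0.375) between stages, the chance of passing both is 89.4% (54 then 144 evaluable per arm) to 90.8% (57 then 152), against the stated 90%. None of that depends on how renal replacement is defined.

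**Inputs for the dilution.**
- 152 per arm at full size, 57 per arm at stage 1 (SAP 1.5).
- *f*, the share on maintenance dialysis at entry: not in the documents. Values of 1%, 2%, 10/152 = 6.6% and 10/57 = 17.5% are assumed. The last two borrow the ten patients in Protocol 7.7 only to give a scale.
- *p*, the risk of new renal replacement in everyone else: assumed 8% on standard of care and 4% on drug.
- No effect of treatment on maintenance dialysis; the same *f* in each arm; unadjusted comparison.

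**Formulas.**
- Observed risk = *f* + (1 − *f*)*p*.
- True OR = (0.04/0.96)/(0.08/0.92) = 0.48.
- Share of standard-of-care events that are prevalent dialysis = *f* / observed risk.
- SD of the chance difference in dialysis share between two arms = sqrt(2*f*(1 − *f*)/152).

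Worked case, *f* = 0.0658: standard of care 0.0658 + 0.9342 × 0.08 = 0.1405; drug 0.0658 + 0.9342 × 0.04 = 0.1032; OR = (0.1032/0.8968)/(0.1405/0.8595) = 0.70.

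| *f* | Observed SOC | Observed drug | Observed OR (true 0.48) | Prevalent share of SOC events | SD of chance imbalance |
|---|---|---|---|---|---|
| 1% | 8.9% | 5.0% | 0.53 | 11% | 1.1 points |
| 2% | 9.8% | 5.9% | 0.58 | 20% | 1.6 points |
| 6.6% | 14.1% | 10.3% | 0.70 | 47% | 2.8 points |
| 17.5% | 24.1% | 20.8% | 0.83 | 73% | 4.4 points |

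The assumed true difference is 4 points, about 6 patients in 152. At *f* = 6.6% the chance imbalance has an SD of 2.8 points, or 4.3 patients.

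**Second set of assumptions.** Relative risk 0.6, *f* = 6.6%, two-sided 0.05 (the plan sets no alpha for secondary endpoints), 152 per arm:

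| New RRT on SOC | True OR | Observed OR, all patients | Power, all patients | Power, non-dialysis only |
|---|---|---|---|---|
| 5% | 0.59 | 0.82 | 8% | 14% |
| 10% | 0.57 | 0.73 | 15% | 24% |
| 15% | 0.56 | 0.68 | 25% | 34% |

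At a 10% rate, the observed OR runs from 0.64 at *f* = 2% to 0.83 at *f* = 17.5%, against a true 0.57.

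**The case against.** **The size is assumed.** The ten patients in Protocol 7.7 trigger a review; they are not a recruitment forecast. If few dialysis patients enrol, the distortion is small: 0.53 against 0.48 at 1%. This stands, and it is why the result is given as a range.

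**The consequence is limited.** Randomisation protects against systematic bias between arms, and the distortion is towards no effect. Renal replacement is one of many secondary outcomes, with no stated power, and it stays weakly powered (14% to 34% in the scenarios above) after the change. All of this stands. The gain is an estimate that answers the stated objective, rather than a well-powered test.

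**Unseen documents may settle it.** SAP I or the case report form guidance could contain a baseline dialysis item or an instruction to record new therapy only. That is possible, but neither the Protocol nor this SAP says so.

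**Stronger readings that the documents do not support.** A reader might infer from the unbracketed grade 8 row in SAP 3.1.1 that a dialysis patient breathing room air is a primary event. Protocol Table 1, SAP 1.1.2, SAP 2.7 and the row's own label all require ventilation for grade 8, so dialysis alone is not one. An intubated dialysis patient would score 8 rather than 7, but both are at or above 5, so the primary dichotomy does not change. A reader might also infer that creatinine is compromised in the same way. It is not: the model adjusts for the baseline value and has a participant intercept, so nobody is scored as a failure. Some dilution and extra variance may remain because dialysis itself drives the values, but the documents give nothing from which to size it.

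**Conclusion.** The point holds for the renal replacement endpoint. Followed as written, the plan counts prevalent dialysis as an event in every arm, while its objective concerns the need for such therapy. With assumed new rates of 8% and 4%, a true odds ratio of 0.48 would appear as 0.53 to 0.83 for a dialysis share of 1% to 17.5%. The share, the rates and the effect are all assumptions, as is the absence of any treatment effect on maintenance dialysis. The harm is dilution, lost precision and chance imbalance, without systematic bias between arms. For creatinine the evidence supports only a sensitivity analysis, and for grade 8 only a clarification of notation. The primary outcome, the stage 1 decision, the error rate and the sample size are not affected.

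**What to change.** 1. In Protocol 3.3 and SAP 1.1.3, 3.2 and 3.2.3, define the endpoint as new renal replacement therapy after randomisation, analysed in participants not on maintenance dialysis at baseline. Report the number on dialysis at baseline by arm.
2. Apply the same definition to the later renal replacement endpoints in the Protocol synopsis and section 3.3.
3. In SAP 3.2.5, keep the all-randomised creatinine model as the main analysis and add a sensitivity analysis without baseline dialysis patients.
4. In the grade 8 row of SAP 3.1.1, add brackets only: (RRT OR ECMO OR inotropic support) AND intubation. This matches the ventilation requirement in Protocol Table 1. Leave the scale itself unchanged, so that SAP and Protocol continue to agree.

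Dialysis patients stay in the primary analysis and in all non-renal analyses. The cost is a denominator for the renal replacement endpoint that is smaller by the dialysis share (about 7% if that share is 6.6%), plus wording changes. If baseline dialysis is not already coded in all arms, it would have to be taken from the medical history collected at screening or from the medical notes.
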